#### 7.2.4.2 Dose Modification for Pembrolizumab

##### 7.2.4.2.1 Dose Modification and Toxicity Management for Immune-related AEs Associated with Pembrolizumab

AEs associated with pembrolizumab exposure may represent an immunologic etiology. These immune-related AEs (irAEs) may occur shortly after the first dose or several months after the last dose of pembrolizumab treatment and may affect more than one body system simultaneously. Therefore, early recognition and initiation of treatment is critical to reduce complications. Based on existing clinical trial data, most irAEs were reversible and could be managed with interruptions of pembrolizumab, administration of corticosteroids, and/or other supportive care. For suspected irAEs, ensure adequate evaluation to confirm etiology or exclude other causes. Additional procedures or tests such as bronchoscopy, endoscopy, or skin biopsy may be included as part of the evaluation. Based on the severity of irAEs, withhold or permanently discontinue pembrolizumab and administer corticosteroids. Dose modification and toxicity management guidelines for irAEs associated with pembrolizumab are provided in [Table 5](#).

**Table 5 Dose Modification and Toxicity Management Guidelines for Immune-related AEs Associated with Pembrolizumab**

General instructions:				
Immune-related AEs	Toxicity grade or conditions (CTCAEv4.0)	Action taken to pembrolizumab	irAE management with corticosteroid and/or other therapies	Monitor and follow-up
Pneumonitis	Grade 2	Withhold	
 
Administer corticosteroids (initial dose of 1-2 mg/kg prednisone or equivalent) followed by taper
 
	
 
Monitor participants for signs and symptoms of pneumonitis
 
Evaluate participants with suspected pneumonitis with radiographic imaging and initiate corticosteroid treatment
 
Add prophylactic antibiotics for opportunistic infections
 

	Grade 3 or 4, or recurrent Grade 2	Permanently discontinue		
Diarrhea / Colitis	Grade 2 or 3	Withhold	
 
Administer corticosteroids (initial dose of 1-2 mg/kg prednisone or equivalent) followed by taper
 
	
 
Monitor participants for signs and symptoms of enterocolitis (ie, diarrhea, abdominal pain, blood or mucus in stool with or without fever) and of bowel perforation (ie, peritoneal signs and ileus).
 
Participants with <math>\geq</math> Grade 2 diarrhea suspecting colitis should consider GI consultation and performing endoscopy to rule out colitis.
 
Participants with diarrhea/colitis should be advised to drink liberal quantities of clear fluids. If sufficient oral fluid intake is not feasible, fluid and electrolytes should be substituted via IV infusion.
 

	Grade 4	Permanently discontinue		

Immune-related AEs	Toxicity grade or conditions (CTCAEv4.0)	Action taken to pembrolizumab	irAE management with corticosteroid and/or other therapies	Monitor and follow-up
AST / ALT elevation or Increased bilirubin	Grade 2	Withhold	
 
Administer corticosteroids (initial dose of 0.5- 1 mg/kg prednisone or equivalent) followed by taper
 
	
 
Monitor with liver function tests (consider weekly or more frequently until liver enzyme value returned to baseline or is stable)
 

	Grade 3 or 4	Permanently discontinue	
 
Administer corticosteroids (initial dose of 1-2 mg/kg prednisone or equivalent) followed by taper
 
	
Type 1 diabetes mellitus (T1DM) or Hyperglycemia	Newly onset T1DM or Grade 3 or 4 hyperglycemia associated with evidence of $\beta$ -cell failure	Withhold	
 
Initiate insulin replacement therapy for participants with T1DM
 
Administer anti-hyperglycemic in participants with hyperglycemia
 
	
 
Monitor participants for hyperglycemia or other signs and symptoms of diabetes.
 

Hypophysitis	Grade 2	Withhold	
 
Administer corticosteroids and initiate hormonal replacements as clinically indicated.
 
	
 
Monitor for signs and symptoms of hypophysitis (including hypopituitarism and adrenal insufficiency)
 

	Grade 3 or 4	Withhold or permanently discontinue 		
Hyperthyroidism	Grade 2	Continue	
 
Treat with non-selective beta-blockers (eg, propranolol) or thionamides as appropriate
 
	
 
Monitor for signs and symptoms of thyroid disorders.
 

	Grade 3 or 4	Withhold or permanently discontinue 		
Hypothyroidism	Grade 2-4	Continue	
 
Initiate thyroid replacement hormones (eg, levothyroxine or liothyroinine) per standard of care
 
	
 
Monitor for signs and symptoms of thyroid disorders.
 

Nephritis and Renal dysfunction	Grade 2	Withhold	
 
Administer corticosteroids (prednisone 1-2 mg/kg or equivalent) followed by taper.
 
	
 
Monitor changes of renal function
 

	Grade 3 or 4	Permanently discontinue		

Immune-related AEs	Toxicity grade or conditions (CTCAEv4.0)	Action taken to pembrolizumab	irAE management with corticosteroid and/or other therapies	Monitor and follow-up
Myocarditis	Grade 1 or 2	Withhold	
 
Based on severity of AE administer corticosteroids
 
	
 
Ensure adequate evaluation to confirm etiology and/or exclude other causes
 

	Grade 3 or 4	Permanently discontinue		
All other immune-related AEs	Intolerable/persistent Grade 2	Withhold	
 
Based on type and severity of AE administer corticosteroids
 
	
 
Ensure adequate evaluation to confirm etiology and/or exclude other causes
 

	Grade 3	Withhold or discontinue based on the type of event. Events that require discontinuation include and not limited to: Gullain-Barre Syndrome, encephalitis		
	Grade 4 or recurrent Grade 3	Permanently discontinue		

1. Withhold or permanently discontinue pembrolizumab is at the discretion of the investigator or treating physician.
 
NOTE:  For participants with Grade 3 or 4 immune-related endocrinopathy where withhold of pembrolizumab is required, pembrolizumab may be resumed when AE resolves to <math>\leq</math> Grade 2 and is controlled with hormonal replacement therapy or achieved metabolic control (in case of T1DM).
				

#### 7.2.4.2.2 Dose Modification and Toxicity Management of Infusion Reactions Related to Pembrolizumab

Pembrolizumab may cause severe or life-threatening infusion reactions including severe hypersensitivity or anaphylaxis. Signs and symptoms usually develop during or shortly after drug infusion and generally resolve completely within 24 hours of completion of infusion. Dose modification and toxicity management guidelines on pembrolizumab-associated infusion reaction are provided in [Table 6](#).

Table 6 Pembrolizumab Infusion Reaction Dose Modification and Treatment Guidelines

NCI CTCAE Grade	Treatment	Premedication at Subsequent Dosing
Grade 1 Mild reaction; infusion interruption not indicated; intervention not indicated	Increase monitoring of vital signs as medically indicated until the participant is deemed medically stable in the opinion of the investigator.	None
Grade 2 Requires therapy or infusion interruption but responds promptly to symptomatic treatment (eg, antihistamines, NSAIDs, narcotics, IV fluids); prophylactic medications indicated for $\leq 24$ h	Stop Infusion. Additional appropriate medical therapy may include but is not limited to: IV fluids Antihistamines NSAIDs Acetaminophen Narcotics  Increase monitoring of vital signs as medically indicated until the participant is deemed medically stable in the opinion of the investigator.  If symptoms resolve within 1 hour of stopping drug infusion, the infusion may be restarted at 50% of the original infusion rate (eg, from 100 mL/h to 50 mL/h). Otherwise dosing will be held until symptoms resolve and the participant should be premedicated for the next scheduled dose.  Participants who develop Grade 2 toxicity despite adequate premedication should be permanently discontinued from further study drug treatment	Participant may be premedicated 1.5h ( $\pm 30$ min) prior to infusion of pembrolizumab with: Diphenhydramine 50 mg PO (or equivalent dose of antihistamine) and/or Acetaminophen 500-1000 mg PO (or equivalent dose of analgesic)

NCI CTCAE Grade	Treatment	Premedication at Subsequent Dosing
Grades 3 or 4  Grade 3: Prolonged (ie, not rapidly responsive to symptomatic medication and/or brief interruption of infusion); recurrence of symptoms following initial improvement; hospitalization indicated for other clinical sequelae (eg, renal impairment, pulmonary infiltrates)  Grade 4: Life-threatening; pressor or ventilatory support indicated	Stop Infusion.  Additional appropriate medical therapy may include but is not limited to:  Epinephrine** IV fluids Antihistamines NSAIDs Acetaminophen Narcotics Oxygen Pressors Corticosteroids  Increase monitoring of vital signs as medically indicated until the participant is deemed medically stable in the opinion of the investigator.  Hospitalization may be indicated.  **In cases of anaphylaxis, epinephrine should be used immediately.  Participant is permanently discontinued from further study drug treatment.	No subsequent dosing

Appropriate resuscitation equipment should be available at the bedside and a physician readily available during the period of drug administration.
 
For further information, please refer to the Common Terminology Criteria for Adverse Events v4.0 (CTCAE) at http://ctep.cancer.gov
		

#### 7.2.4.2.3 Other allowed dose interruption(s) for pembrolizumab

Pembrolizumab may be interrupted for situations other than treatment-related AEs such as medical / surgical events or logistical reasons not related to study treatment. Participants should be placed back on study therapy within 3 weeks of the scheduled interruption, unless otherwise discussed with the Sponsor. The reason for interruption should be documented in the patient's study record.

### 7.3 Method of Treatment Assignment

Study treatment will be allocated via IVRS. Each new dose level will open for enrollment without delay once the 42-day DLT observation period of the previous dose cohort is completed, and a dose escalation decision is made.

#### 7.3.1 Stratification

No stratification based on age, sex or other characteristics will be used in this trial.

## **7.4 Blinding**

This is an open-label trial; therefore, the Sponsor, investigator and participant will know the treatment administered.

## **7.5 Preparation/Handling/Storage/Accountability**

### **7.5.1 Dose Preparation**

The rationale for selection of doses to be used in this trial is provided in Section 5.5.1. There are no specific calculations or evaluations required to be performed in order to administer the proper dose to each participant.

### **7.5.2 Handling, Storage and Accountability**

The investigator or designee must confirm appropriate temperature conditions have been maintained during transit for all study treatment received and any discrepancies are reported and resolved before use of the study treatment.

Only participants enrolled in the study may receive study treatment and only authorized site staff may supply or administer study treatment. All study treatments must be stored in a secure, environmentally controlled, and monitored (manual or automated) area in accordance with the labeled storage conditions with access limited to the investigator and authorized site staff.

The investigator, institution, or the head of the medical institution (where applicable) is responsible for study treatment accountability, reconciliation, and record maintenance (ie, receipt, reconciliation, and final disposition records).

For all trial sites, the local country Sponsor personnel or designee will provide appropriate documentation that must be completed for drug accountability and return, or local discard and destruction if appropriate. Where local discard and destruction is appropriate, the investigator is responsible for ensuring that a local discard/destruction procedure is documented.

The trial site is responsible for recording the lot number, manufacturer, and expiry date for any locally purchased product as per local guidelines unless otherwise instructed by the Sponsor.

The investigator shall take responsibility for and shall take all steps to maintain appropriate records and ensure appropriate supply, storage, handling, distribution and usage of study treatments in accordance with the protocol and any applicable laws and regulations.

## **7.6 Treatment Compliance**

Compliance will be assessed at each clinic visit.

All doses of pembrolizumab will be administered under the supervision of a qualified physician and/or qualified designee experienced in the use of anticancer agents.

Interruptions from the protocol specified treatment plan for >12 weeks between MK-7162 or pembrolizumab doses for non-drug related or administrative reasons require consultation

between the investigator and the Sponsor and written documentation of the collaborative decision on participant management.

## **7.7 Concomitant Therapy**

Medications or vaccinations specifically prohibited in the exclusion criteria are not allowed during the ongoing trial. If there is a clinical indication for any medication or vaccination specifically prohibited during the trial, discontinuation from trial therapy or vaccination may be required. The investigator should discuss any questions regarding this with the Sponsor Clinical Director. The final decision on any supportive therapy or vaccination rests with the investigator and/or the participant's primary physician. However, the decision to continue the participant on study treatment requires the mutual agreement of the investigator, the Sponsor and the participant.

### **7.7.1 Acceptable Concomitant Medication**

All treatments that the investigator considers necessary for a participant's welfare may be administered at the discretion of the investigator in keeping with the community standards of medical care except for those that are prohibited as described in Section 7.7.2. All concomitant medication will be recorded on the case report form (CRF) including all prescription, over-the-counter (OTC), herbal supplements, and IV medications and fluids. If changes occur during the trial period, documentation of drug dosage, frequency, route, and date should also be included on the CRF.

All concomitant medications received within 28 days before the first dose of trial treatment and 30 days after the last dose of trial treatment should be recorded. Concomitant medications administered more than 30 days after the last dose of trial treatment should be recorded for SAEs and events of clinical interest (ECIs) as defined in Section 9.3. The investigator or qualified designee will record medication, if any taken by the participant during the trial.

### **7.7.2 Prohibited Concomitant Medications**

Participants are prohibited from receiving the following therapies during the Screening and Treatment Phases (including retreatment for post-complete response relapse) of this trial:

- Antineoplastic biological therapy not specified in this protocol
- Immunotherapy not specified in this protocol
- Chemotherapy not specified in this protocol
- Investigational agents not specified in this protocol
- Radiation therapy

Note: Palliative radiation therapy to a symptomatic solitary lesion or to the brain may be allowed at the investigator's discretion, but only after the DLT observation period in order for the participant to be considered evaluable for DLT.

- Live vaccines within 30 days prior to the first dose of trial treatment and while participating in the trial. Examples of live vaccines include, but are not limited to, the following: measles, mumps, rubella, varicella/zoster, yellow fever, rabies, Bacillus Calmette-Guérin (BCG), and typhoid vaccine. Seasonal influenza vaccines for injection are generally killed virus vaccines and are allowed; however, intranasal influenza vaccines (eg, FluMist®) are live attenuated vaccines and are not allowed.
- Systemic glucocorticoids for any purpose other than to modulate symptoms from an AE of suspected immunologic etiology. Physiologic doses of corticosteroids may be administered, but only after consultation with and approval by the Sponsor.
- MAO-inhibitors (MAOI) or any drug which has significant MAOI activity (eg, meperidine, linezolid, methylene blue)

Participants who, in the assessment by the investigator, require the use of any of the aforementioned treatments for clinical management should be removed from the trial.

Participants may receive other medications that the investigator deems to be medically necessary.

Treatment by local surgery (and/or radiation therapy) of isolated or symptomatic progressing lesions in the setting of improving baseline disease may be permitted for palliative or potentially curative management following completion of Cycle 2. All such interventions, including continuation of study treatment, should be discussed with the Sponsor.

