Participants may receive study medication for up to 36 cycles. Participants will be treated until progressive disease, unacceptable toxicity, intercurrent illness that prevents further administration of treatment, Investigator's decision to withdraw treatment, participant withdrawal of consent, pregnancy of the participant, noncompliance with study medication or procedure requirements, participant completes treatment, or administrative reasons requiring cessation of treatment, at which point they will be discontinued from the study.

All participants will be followed for at least 30 days after their last dose of MK-7162 for AE monitoring. Serious adverse events will be collected for 90 days after discontinuation, 30 days if the participant initiates new anticancer therapy less than 30 days after study treatment discontinuation, or the day new anticancer therapy is initiated if between 30 days and 90 days after study treatment discontinuation. Participants with an ongoing AE of Grade  $> 1$  at the time of treatment discontinuation will be followed until resolution of the AE to Grade 0-1, until considered stable by the treating physician, or until beginning a new anticancer therapy, whichever occurs first.

Participants who discontinue treatment for reasons other than confirmed progressive disease will have post-treatment follow-up for disease status (including imaging) until disease progression, initiating a new anticancer therapy, withdrawing consent for study participation, or becoming lost to follow-up.

After confirmed disease progression, each participant who discontinues treatment will be contacted by telephone every 12 weeks ( $\pm 14$  days) for survival until withdrawal of consent to participate in the study, becoming lost to follow-up, death, or end of the study, whichever occurs first.

Specific procedures to be performed during the trial, as well as their prescribed times and associated visit windows, are outlined in the Trial SoA - Section 2. Details of each procedure are provided in Section 9 – Study Assessments and Procedures.

This trial will use an adaptive design based on prespecified criteria. Interim analyses will be conducted to examine clinical trial data on a continuous basis to allow for dose-finding decisions, safety, tolerability, and efficacy analysis.

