## **8. Discontinuation/Withdrawal Criteria**

### **8.1 Discontinuation of Study Treatment**

Discontinuation of study treatment does not represent withdrawal from the study.

As certain data on clinical events beyond study treatment discontinuation may be important to the study, they must be collected through the participant's last scheduled follow-up, even if the participant has discontinued study treatment. Therefore, all participants who discontinue study treatment prior to completion of the protocol-specified treatment period will still continue to participate in the study as specified in Section 2 - SoA and Section 9.11.3 – Discontinued Participants Continuing to be Monitored in the Study.

Participants may discontinue study treatment at any time for any reason or be dropped from the study treatment at the discretion of the investigator should any untoward effect occur. In addition, a participant may be discontinued from study treatment by the investigator or the Sponsor if study treatment is inappropriate, the trial plan is violated, or for administrative and/or other safety reasons. Specific details regarding procedures to be performed at study treatment discontinuation are provided in Section 9.1.9 – Withdrawal/Discontinuation.

A participant must be discontinued from study treatment but continue to be monitored in the study for any of the following reasons:

- The participant or participant's legally acceptable representative requests to discontinue study treatment.
- The participant interrupts study medication administration for more than 12 consecutive weeks.
- The participant interrupts MK-7162 for more than 84 (QD) cumulative missed doses.
- The participant has a medical condition or personal circumstance which, in the opinion of the investigator and/or sponsor, places the participant at unnecessary risk from continued administration of study treatment.
- The participant has a confirmed positive serum or urine pregnancy test.
- Non-compliance with trial treatment or procedure requirements.
- Confirmed radiographic disease progression outlined in Section 9.11 – Visit Requirements (Exception is if Sponsor approves treatment continuation).
- Unacceptable adverse experiences as described in Section 9.3 – Adverse Events, Serious Adverse Events and Other Reportable Safety Events.
- Intercurrent illness other than another malignancy as noted above (Section 5.1.1 – Dose Escalation and Confirmation) that prevents further treatment administration.

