#### **9.1.5.2 Concomitant Medications**

The investigator or qualified designee will record medication, if any, taken by the participant during the trial.

All medications related to reportable SAEs and ECIs should be recorded as defined in Section 9.3 (Adverse Events, Serious Adverse Events and Other Reportable Safety Events).

All new anticancer therapy initiated after the study start must be recorded in the eCRF. If a participant initiates another anticancer therapy other than the assigned study treatment(s), the study treatment(s) should be discontinued and the participant will move into the survival follow-up phase; if a participant initiates a new anticancer therapy within 30 days after the last dose of the trial treatment, the 30-day Safety Follow-up visit should occur before the first dose of the new therapy.

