#### **9.5.4.2 Pregnancy Test**

All women who are being considered for participation in the trial, and who are not surgically sterilized or postmenopausal, must be tested for pregnancy within 72 hours prior to first dose of study treatment. If a urine test is positive or not evaluable, a serum test will be required. Participants must be excluded/discontinued from the study in the event of a positive test result. Pregnancy test (such as monthly testing) may be conducted if required by local regulations.

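### Section 7.7.2 removes participants who need a prohibited therapy from the trial, while Sections 8.1, 8.2, 9.1.5.2 and 9.10.3 keep anyone who stops treatment in follow-up unless consent is withdrawn

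*Combined protocol and SAP*

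**What the plan says.** Section 7.7.2 lists therapies not allowed during screening and treatment: off-protocol anticancer drugs, investigational agents, radiation with exceptions, live vaccines, systemic glucocorticoids outside stated uses, and drugs with MAOI activity such as linezolid. It then says that participants who, in the investigator's assessment, "require the use of any of the aforementioned treatments for clinical management should be removed from the trial".

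Other sections take a different line:

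- Section 8.1: "Discontinuation of study treatment does not represent withdrawal from the study". Everyone who stops treatment early stays in the study for the scheduled follow-up.
- Section 8.2: the only event that obliges study withdrawal is withdrawal of consent. Scheduled visits then end.
- Section 9.1.5.2, for a participant who starts another anticancer therapy: "the study treatment(s) should be discontinued and the participant will move into the survival follow-up phase".
- Sections 9.10.3 to 9.10.3.2: a Discontinuation Visit whatever the reason for stopping, a mandatory Safety Follow-up Visit at about 30 days, and survival calls every 12 weeks after confirmed progression or new anticancer therapy.
- Section 7.7, the parent of 7.7.2, says of a clinical need for a prohibited medication only that "discontinuation from trial therapy or vaccination may be required", and it leaves room for continued treatment by mutual agreement.

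Two further sentences use study-exit wording. Section 5.1.1 ends its list of stopping reasons with "administrative reasons requiring cessation of treatment, at which point they will be discontinued from the study". Section 9.5.4.2 says: "Participants must be excluded/discontinued from the study in the event of a positive test result".

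**The concern.** Whether a participant is on treatment and whether the participant is in the study are separate facts, and the follow-up data depend on the second. Section 7.7.2 merges them for a group selected by clinical events: an infection, a need for steroids, a need for other cancer treatment. If a site acts on 7.7.2, safety observation ends when the participant's condition has just changed, so the missing data are unlikely to be missing at random. Safety and DLTs are the primary endpoints. Another site that applies 8.1 would follow the same participant fully, so what is collected would depend on which section each site reads.

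**Working it through.** No formula tests this point. It rests on reading the sections side by side, with a little arithmetic on the DLT window.

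**1. What removal means.** Section 7.7.2 does not define it. The only section that describes leaving the study is 8.2: no further treatment and no scheduled visits. Section 9.3.1 adds that investigators need not actively look for events in former participants.

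**2. A participant who needs off-protocol anticancer therapy.** Under 7.7.2 the participant leaves the trial. Under 9.1.5.2 and 9.10.3.2 the participant stops treatment, has the safety visit (before the new therapy if that starts within 30 days) and receives 12-weekly survival calls. This is a direct contradiction for one person. The serious adverse event (SAE) collection at stake is less than the full 90 days if the new therapy starts within that time: 5.1.1 shortens the window to 30 days, or to the day the new therapy starts if that falls between Days 30 and 90.

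**3. A participant who needs another listed therapy, for example linezolid for an infection, and whose study treatment stops.** Under 7.7.2 follow-up ends. Under 8.1, 9.10.3 and 5.1.1 the participant has the Discontinuation Visit, the safety visit, SAE collection to 90 days and, under 9.2.4, imaging every 9 weeks if there is no documented progression. Survival calls are not yet due, because they begin only at confirmed progression or new anticancer therapy.

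**4. The DLT window.** Two 21-day cycles give 2 × 21 = 42 days. Suppose removal on Day 20.

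- Unobserved part of the window: 42 − 20 = 22 days.
- Section 6.5 replaces a participant who leaves the trial before completing the safety evaluations for a reason other than a treatment-related AE.
- Section 10.5.1 counts any treated participant who has a DLT before Day 42. If the participant stays under observation, a DLT in those 22 days enters the count.
- In Table 1, 0 of 3 is escalate and 1 of 3 is stay, so one unseen DLT can change a dose decision.

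The evaluability denominator alone is seldom at stake. Section 6.5 also excludes anyone without a DLT who received less than 90% of the planned dosing: 0.90 × 42 = 37.8, so at least 38 daily MK-7162 doses are needed. A participant who stops earlier without a DLT is non-evaluable under either reading.

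**5. The lesser conflicts.** Section 5.1.1 follows its study-exit sentence with "All participants will be followed for at least 30 days after their last dose of MK-7162 for AE monitoring", and then with SAE collection, imaging follow-up and survival calls. It contradicts itself but does not remove follow-up. Section 9.5.4.2 conflicts with 8.1, which lists a positive test as a reason to stop treatment while monitoring continues, and with 6.3.3, which stops study treatment only and requires at least monthly contact.

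**6. The cross-reference.** Section 8.1 twice sends the site to 9.11.3 for participants who are off treatment but still monitored. That text is numbered 9.10.3.

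**The case against.** The best defence is that 8.1 and 8.2 are the dedicated sections and should govern. Section 7.7 speaks of stopping therapy, so 7.7.2 can be read as a loose way of saying the same. That is probably what was meant, but 7.7.2 does not say so, and the pointer in 8.1 leads to a section number that does not exist.

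The following mitigations stand and limit the size:

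- Section 9.1.9 requires final-visit activities at withdrawal and follow-up of AEs then present. It does not cover events that start later.
- Under 9.3.1, drug-related SAEs that come to the investigator's attention are reportable at any time. Non-serious events and SAEs not considered drug-related are not covered.
- Overall survival is exploratory, in an open-label study without a control arm.
- The DLT consequence rests on 10.5.1. Section 5.1.1 defines evaluability more narrowly, as completing both cycles or stopping treatment because of a DLT. A DLT that arises after treatment stopped for another reason does not clearly fit that definition.

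A reader might infer from 5.1.1 that nearly every participant who stops treatment loses follow-up. The documents do not support this, because the next paragraphs of 5.1.1 require follow-up. A reader might also infer that pregnant participants are lost. They are not: 9.5.4.2 begins with pre-dose testing, and on-treatment pregnancy is followed under 6.3.3 and 9.3.6. Nor does each affected participant lose a full 90 days of SAE collection and all survival contacts, as steps 2 and 3 show.

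**Conclusion.** The contradiction between 7.7.2 and Sections 8.1, 8.2, 9.1.5.2 and 9.10.3 to 9.10.3.2 is real and should be corrected. A site that applies 7.7.2 literally would lose AEs and SAEs that start after removal, later disease or survival follow-up where due, and a DLT between removal and Day 42. The conflicts in 5.1.1 and 9.5.4.2 are wording faults with little practical effect.

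The documents give no rate for need of a prohibited therapy. On an assumed 5% to 20% of the approximately 40 Part A participants, 0.05 × 40 = 2 to 0.20 × 40 = 8 would be exposed to the conflict. That is a ceiling on data loss, since it also requires the site to follow 7.7.2 rather than 8.1. The documents do not support a claim of demonstrable bias in the AE tables or in survival; they support a risk of avoidable, outcome-related loss of follow-up.

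**What to change.** State in 7.7.2, in the treatment-duration paragraph of 5.1.1 and, for tests after the first dose, in 9.5.4.2 that the participant remains in the study and is followed under Sections 8.1 and 9.10.3 unless consent is withdrawn under 8.2. Correct both references in 8.1 from 9.11.3 to 9.10.3.

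Sections 7.7 and 7.7.2 also differ on whether needing a prohibited therapy means that study treatment must stop. The sponsor must reconcile those passages; no rule is proposed here.

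The cost is a wording change in three sections plus the cross-reference. The visits are already in the Schedule of Activities, so no procedure is added.
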